#### **4.2.2. Subject Completion**

A subject will be considered to have completed the study when the subject has completed all study related procedures or dies or withdraws consent. Subjects will continue to be enrolled in this study and receive study treatment until the subject qualifies for Permanent Discontinuation for Study Treatment (See Section 4.2.1).

The cause of death must be documented in the eCRF. A subject will be considered to have withdrawn from the study if the subject has not died and is lost to follow-up, has withdrawn consent, or if the study is closed/terminated.

### **5. STUDY TREATMENTS**

The term ‘study treatment’ is used throughout the protocol to describe any combination of products received by the subject as per the protocol design. Study treatment may therefore refer to the individual study treatments or the combination of those study treatments. However, for the purpose of this study investigational product will only refer to eltrombopag.

#### **5.1. Eltrombopag (SB-497115) Novartis Investigational Product**

Eltrombopag will be provided to sites by Novartis.

Based upon the supply of eltrombopag used in the parent study, subjects may be dosed with eltrombopag tablets or powder for oral suspension (PfOS). Subjects who had received eltrombopag powder for oral suspension in the parent study may switch to tablets in the rollover study if relevant criteria are met based upon the parent study (e.g., are age-appropriate to receive tablets). If there is a switch from oral suspension to tablets, the doses should take into account the differences in bioavailability between formulations. In a relative bioavailability study conducted under fasted conditions in healthy adult subjects, the eltrombopag PfOS formulation delivered 22% higher plasma eltrombopag AUC(0-∞) and 30% higher Cmax compared to the tablet formulation.

##### **Eltrombopag Tablets**

Eltrombopag tablets will be white, round film coated tablets containing eltrombopag olamine equivalent to 12.5 mg, 25 mg, 50 mg, 75 mg and 100 mg of eltrombopag. The 12.5 mg tablet will be smaller than the 25 mg, 50 mg, 75 mg and 100 mg tablets.

Tablets will be packaged in white high density polyethylene (HDPE) bottles with white plastic, induction-seal child-resistant caps. Each bottle will contain 35 tablets. The contents of the label will be in accordance with all applicable regulatory requirements.

##### **Eltrombopag Powder for Oral Suspension**

Eltrombopag powder for oral suspension (Eltrombopag PfOS) is a reddish-brown to yellow powder contained inside an elongated sachet. Each sachet will contain eltrombopag olamine equivalent to 20 mg of eltrombopag per gram of powder.

PfOS sachets will be packaged in a carton. Each carton pack will hold 35 sachets along with a plastic reconstitution container and a syringe-adapt cap. The pack will also contain an extra syringe-adapt cap as a spare. The clinical site will provide a 10cc syringe with each carton.

The sachet should not be opened until ready to use. Add 9.5 mL of water drawn using a 10cc syringe into the provided plastic container. Cut open the sachet and add the entire content of the sachet into the container with water. The container is capped and shaken for 10-20 seconds. The resulting suspension contains 2 mg/mL of eltrombopag dose. The prescribed volume (dose) is drawn through the syringe port on the cap with a syringe. Upon dosing, the rest of the remaining suspension in the container is discarded. The container and the syringe are rinsed with water and dried.

If the prescribed dose is > 24 mg, which will require that part or all of a second sachet be used, then the suspension can be prepared by adding the contents of the two sachets to 19.0 mL of water, and then following the steps outlined above. The water has to be drawn by using the 10cc syringe twice, and similarly dosing has to occur by using the same 10cc syringe twice.

A fresh dose is prepared everyday just prior to the dosing and no storage of the reconstituted suspension is allowed. Eltrombopag will be provided to sites by Novartis. The contents of the label will be in accordance with all applicable regulatory requirements.

Under normal conditions of handling and administration, investigational product is not expected to pose significant safety risks to site staff. A Material Safety Data Sheet (MSDS) describing the occupational hazards and recommended handling precautions will be provided to site staff if required by local laws or will otherwise be available from Novartis upon request.

## **5.2. Eltrombopag Dosage and Administration**

Site personnel will instruct the subjects (and their parents/guardians if applicable) on how to take their medication. Every effort should be made to encourage subject compliance with the dosage regimen as per protocol.

Study treatment will be dispensed in either bottles containing 35 tablets each, or packs containing 35 unit-dose sachets each. Additional tablets or packs of sachets will be dispensed when the site personnel determine the current supply will not be sufficient until the next study visit.

Study treatment compliance will be assessed as described in Section 5.9. For subjects who receive PfOS, study treatment compliance will be assessed at each visit as described in Section 5.9. All subjects/parents/guardians should be instructed to bring all bottles or sachets with any unused drug to each visit with the investigator.

### 5.2.1. Dietary Restrictions

Eltrombopag should be taken at least four hours before or after any products such as antacids, dairy products, or mineral supplements containing polyvalent cations (e.g. aluminium, calcium (see below), iron, magnesium, selenium and zinc).

Eltrombopag may be taken either on an empty stomach (1 hour before or 2 hours after a meal) or with food containing little (< 50 mg) or preferably no calcium or dairy products

Administration of eltrombopag with a polyvalent cation-containing antacid decreased plasma eltrombopag exposure by 70%, and a similar reduction was observed when eltrombopag was administered with a high-calcium meal [GlaxoSmithKline Document Number UM2005/00217/08]. Therefore, every effort must be made to educate subjects on how to take study medication with medications or foods containing these polyvalent cations. Details of these and all concomitant medications should be recorded in the eCRF.

### 5.3. Eltrombopag Starting Dose

All subjects will receive eltrombopag at the dose that they were receiving at the time of the Transition Visit, except in the case where the subject required a dose modification in the parent study or unless adjustments are warranted according to the dosing guidelines.

### 5.4. Dose Adjustments

Each subject's dose of study treatment will be adjusted as needed following the provided dosing guidelines and based upon their individual platelet response.

The investigator may also make dose adjustments based on safety assessments (e.g. for adverse event or other safety assessments, provided the discontinuation criteria are not met (see Section 5.4.1)). **Dosage must never exceed the maximum dose allowed by the parent study.**

Instructions for dose adjustments throughout the duration of the study are described in Table 1, Table 2, Table 3, and Table 4.

#### 5.4.1. Cohort A (MDS/AML Adult Subjects)

The range of doses of eltrombopag that will be used in this cohort are 50 mg to 300 mg once daily for subjects of non- East Asian heritage. The dose ranges for subjects of East Asian heritage (i.e. Japanese, Chinese, Taiwanese, Thai and Korean) will be 25 mg to 150 mg.

The dose of eltrombopag can be increased every 2 weeks by 100 mg (50 mg for subjects of East Asian heritage) until maximum 300 mg per day (150 mg for subjects of East Asian heritage). Dose adjustments will be dependent on each subject's platelet counts; adjusted to maintain platelet counts  $\geq 100$  Gi/L, and dose reduced for platelet counts  $>400$  Gi/L.

If dose increases or decreases are required based upon the dose adjustment guidelines in Table 1, subjects must return the previous bottle(s) and may be dispensed new bottles containing 35 tablets each. Site personnel will instruct subjects on any modified dosing instructions (i.e. take 2 or 3 tablets per day based on required dose) based upon dose adjustment guidelines below.

The maximum dose will be 300 mg once daily (150 mg daily for subjects of East Asian heritage) and must never exceed the maximum dose allowed by the parent study.

Subsequent dose adjustments will be based upon platelet counts and safety. If dose increases or decreases are required based upon platelet counts, site personnel will instruct subjects on modified dosing instructions based upon the guidelines in Table 1.

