#### **5.4.1.1. Dose Escalation**

Intra-individual dose adjustments will be made in a stepwise fashion, by sequentially increasing from 50 mg to the 100 mg to the 200 mg and 300 mg eltrombopag dose levels as needed depending upon platelet counts (dose levels will be reduced by 50% for subjects of East Asian heritage i.e., 25 mg, 50 mg, 100 mg and 150 mg, respectively).

Subsequent dose adjustments will be based upon platelet counts and safety (Table 1). If dose increases or decreases are required based upon platelet counts, site personnel will instruct subjects on modified dosing instructions based upon the guidelines in Section 5.4.1.

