**Table 1 Dose Adjustment Guidelines for Adult MDS/AML Patients a**

Platelet counts <100 Gi/L	Increase daily dose to the next dose level.b Wait for 2 weeks to see the effect of the dose increase on platelet counts before another dose increase is considered.
Platelet counts 100-400 Gi/L	Maintain dose.
Platelet counts >400 Gi/L	Decrease daily dose.b If platelet counts remain >400 Gi/L, wait for 2 weeks to see the effect of the dose decrease on platelet counts before another dose decrease is considered.

**Subjects who have disease progression and also experience clinical benefit will be allowed to continue treatment with study medication, provided that in the investigator judgement the benefit-risk ratio of continuing treatment with study medication is favorable. Given that blasts can be leukemic or benign, blasts counts alone must not be the sole indicator of disease progression: rather, the totality of the available data must be considered when determining whether subjects are receiving clinical benefit or not.**

- a. After any dose adjustment, monitor platelet counts at least weekly for 4 weeks. The investigator may also make dose adjustments based on safety assessments (e.g. for adverse event or other safety assessments, provided the discontinuation criteria are not met [see Section 4.2]). Use the dose levels outlined in Section 5.4.1.1. and in Section 5.4.1.2. for dose adjustments. Investigators may use their clinical judgment in modifying the schedule of eltrombopag if used as monotherapy or in combination with chemotherapy or disease modifying therapies to treat underlying MDS or AML.
- b. See Section 5.4.1. for dose escalation or reduction for further details.

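### Cohort A: the fixed 100 mg (50 mg East Asian) increase in Protocol 5.4.1 contradicts the 5.4.1.1 dose ladder at the lowest dose level

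*Protocol*

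**What the plan says.** Protocol Section 5.4.1 opens with the dose range for subjects not of East Asian heritage: "The range of doses of eltrombopag that will be used in this cohort are 50 mg to 300 mg once daily". For East Asian subjects the range is 25 to 150 mg. It then gives an escalation rule: "The dose of eltrombopag can be increased every 2 weeks by 100 mg (50 mg for subjects of East Asian heritage", up to a maximum of 300 mg (150 mg) per day.

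Section 5.4.1.1 describes escalation as stepwise, "by sequentially increasing from 50 mg to the 100 mg to the 200 mg and 300 mg eltrombopag dose levels", with each level halved for East Asian subjects (25, 50, 100 and 150 mg).

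Table 1, for platelet counts below 100 Gi/L, says "Increase daily dose to the next dose level". Its footnote a adds "Use the dose levels outlined in Section 5.4.1.1. and in Section 5.4.1.2. for dose adjustments". Its footnote b adds "See Section 5.4.1. for dose escalation or reduction for further details". Section 5.4.1.1 closes in the same direction: "site personnel will instruct subjects on modified dosing instructions based upon the guidelines in Section 5.4.1".

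**The concern.** Two escalation rules stand next to each other, one as a fixed increment and one as a list of levels. They cannot both be right at the bottom of the range, because the gap between the first two listed levels is half the stated increment. The lowest level is not hypothetical: Section 5.4.1 itself names 50 mg (25 mg) as the bottom of the Cohort A range.

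What is at stake is the dose given to an individual subject. Starting from 50 mg, a site following the increment sentence would pass over 100 mg, the dose at which the parent MDS/AML study started (Section 1.1.3). The result would not look wrong at the pharmacy: it is under the Cohort A maximum and can be made up from the tablets in Section 5.1 (100 + 50 = 150 mg; one 75 mg tablet for East Asian subjects).

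**Working it through.** **Inputs**
- Increment: +100 mg, or +50 mg East Asian (Section 5.4.1).
- Maximum: 300 mg, or 150 mg East Asian (Section 5.4.1).
- Ladder: 50, 100, 200, 300 mg, or 25, 50, 100, 150 mg East Asian (Section 5.4.1.1).

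**Check.** At each level, compare min(dose + increment, maximum) with the next listed level.

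| Group | From | Fixed increment | Ladder | Agree? |
|---|---|---|---|---|
| Not East Asian | 50 mg | 50 + 100 = 150 mg | 100 mg | No |
| Not East Asian | 100 mg | 100 + 100 = 200 mg | 200 mg | Yes |
| Not East Asian | 200 mg | 200 + 100 = 300 mg | 300 mg | Yes |
| East Asian | 25 mg | 25 + 50 = 75 mg | 50 mg | No |
| East Asian | 50 mg | 50 + 50 = 100 mg | 100 mg | Yes |
| East Asian | 100 mg | 100 + 50 = 150 mg | 150 mg | Yes |

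The rules disagree at 1 of 3 steps in each group, always the lowest.

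**Size at that step.** 150/100 = 75/50 = 1.5, so the fixed rule gives 1.5 times the ladder dose. Against the starting dose it is 150/50 = 3 rather than 100/50 = 2.

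**Carry-over.** Applied repeatedly from the lowest level, the increment gives 50, 150, 250, 300 mg (25, 75, 125, 150 mg), with the last step cut off at the maximum. The second increase is therefore off the ladder too: 250 against 200 mg (125 against 100 mg). Both routes reach the maximum on the third increase, so the excess is 50 mg (25 mg) after each of the first two increases and nil after the third.

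**Likely origin.** The parent study started at 100 mg (50 mg) with a maximum of 300 mg (150 mg). Over that range the increment and the ladder coincide. The sentence works there and fails only once 50 mg (25 mg) is added below it. This is an inference; the documents do not explain the sentence.

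**Which rule governs**
- For the ladder: Section 5.4 says that dose-adjustment instructions are in Tables 1 to 4. Section 5.4.1 itself defers to Table 1 twice. Table 1 moves by level, and footnote a sends the reader to 5.4.1.1. Section 5.4.1.1 is directive, whereas the increment sentence is only permissive.
- For the increment: footnote b and the end of 5.4.1.1 refer the reader to Section 5.4.1. That number also covers 5.4.1.1 to 5.4.1.3, so these references need not mean the increment sentence.

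The balance favours the ladder.

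**Footnote a.** It also cites 5.4.1.2 for dose levels. Section 5.4.1.2 says when to reduce but lists no levels.

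**The case against.** The strongest reply is that the protocol already answers the question. Section 5.4, Table 1, footnote a and 5.4.1.1 all lead to 100 mg (50 mg), so the error needs a site to act on one permissive sentence and overlook the rest. This stands, and it limits the point to a wording error. A reader might infer that nothing else in the dosing text blocks the 150 mg step. The documents do not support that: the ladder and Table 1 are themselves dosing text and direct otherwise.

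A reader might also infer that a subject at the lowest level with a count above 400 Gi/L is left unhandled, since a decrease is mandatory and no lower level is listed. That goes too far. Section 5.4.1.3 permits temporary interruption, footnote a leaves the schedule to clinical judgment, and Section 3.2.4 sends dose uncertainties to the Medical Lead. An explicit every-other-day step, as Table 2 gives for its lowest ITP dose, would be added detail. Its absence is not an error.

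Exposure is also limited. Footnote a requires close follow-up ("After any dose adjustment, monitor platelet counts at least weekly for 4 weeks"), and 5.4.1.2 allows an early reduction, even within 2 weeks of a change. The parent study's starting dose was above the lowest level, and only 22 subjects will be analysed across both cohorts (SAP Section 1).

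None of this makes the sentence correct. It remains a stated dosing rule that produces an unlisted dose.

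**Conclusion.** The increment sentence in Section 5.4.1 is wrong as written for the lowest Cohort A level: it gives 150 mg instead of 100 mg (75 instead of 50 mg for East Asian subjects), at one of three steps. The ladder governs on the better reading, but a site relying on the sentence could triple the dose where a doubling is meant. The faulty pointer in footnote a is a minor drafting slip, because 5.4.1.1 already lists every level needed to step down.

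The arithmetic uses only stated doses. That the ladder is the intended rule is a judgement from the weight of the cross-references. The number of subjects at the lowest level is not given, and nothing shows that a 50 to 150 mg step took place. The study is descriptive and tests no hypotheses (Protocol Section 10.1), so no conclusion changes.

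A reader might infer that the planned listing of protocol deviations (SAP Section 2.4.1) should now declare the ladder as the governing rule. That would be unwise: it would set a rule after the last visit and could mark as a deviation a step that Section 5.4.1 literally permits.

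**What to change.** In Section 5.4.1, keep the two-week interval and the maximum, and replace the fixed increment with wording such as: *to the next dose level in Section 5.4.1.1*. One phrase then holds for both heritage groups at every step.

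As a tidy-up, state in Section 5.4.1.2 that reductions follow the same ladder in reverse: 300, 200, 100, 50 mg (150, 100, 50, 25 mg for East Asian subjects). Footnote a's pointer then leads to actual dose levels.

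The cost is two small wording changes, with no new dose level, visit, assessment or analysis. Last patient last visit was on 23-Feb-2022 (SAP Section 1), so the change cannot alter this study and is for any successor protocol that reuses the text. The SAP needs no change.

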#### **5.4.1.1. Dose Escalation**

Intra-individual dose adjustments will be made in a stepwise fashion, by sequentially increasing from 50 mg to the 100 mg to the 200 mg and 300 mg eltrombopag dose levels as needed depending upon platelet counts (dose levels will be reduced by 50% for subjects of East Asian heritage i.e., 25 mg, 50 mg, 100 mg and 150 mg, respectively).

Subsequent dose adjustments will be based upon platelet counts and safety (Table 1). If dose increases or decreases are required based upon platelet counts, site personnel will instruct subjects on modified dosing instructions based upon the guidelines in Section 5.4.1.

#### **5.4.1.2. Dose Reduction**

Subjects whose platelet count exceeds 400 Gi/L at any point during the treatment period must decrease the dosage of study medication. Temporary dose reduction of study medication may also be made by the investigator (i.e. to allow for recovery of AEs) as per Table 1 and Section 5.4.1.3.

If a subject's platelet count increases significantly and if the investigator thinks a dose reduction is medically appropriate, the dose can be decreased even if the platelet count is below 200 Gi/L or a dose modification was done less than 2 weeks before.

#### **5.4.1.3. Dose Interruption**

Temporary interruptions of study medication may be made by the investigator (e.g. to allow for recovery of AEs).

Refer to Section 4.2.1 for criteria for permanent discontinuation of study medication.

**Table 1 Dose Adjustment Guidelines for Adult MDS/AML Patients a**

Platelet counts <100 Gi/L	Increase daily dose to the next dose level.b Wait for 2 weeks to see the effect of the dose increase on platelet counts before another dose increase is considered.
Platelet counts 100-400 Gi/L	Maintain dose.
Platelet counts >400 Gi/L	Decrease daily dose.b If platelet counts remain >400 Gi/L, wait for 2 weeks to see the effect of the dose decrease on platelet counts before another dose decrease is considered.

**Subjects who have disease progression and also experience clinical benefit will be allowed to continue treatment with study medication, provided that in the investigator judgement the benefit-risk ratio of continuing treatment with study medication is favorable. Given that blasts can be leukemic or benign, blasts counts alone must not be the sole indicator of disease progression: rather, the totality of the available data must be considered when determining whether subjects are receiving clinical benefit or not.**

- a. After any dose adjustment, monitor platelet counts at least weekly for 4 weeks. The investigator may also make dose adjustments based on safety assessments (e.g. for adverse event or other safety assessments, provided the discontinuation criteria are not met [see Section 4.2]). Use the dose levels outlined in Section 5.4.1.1. and in Section 5.4.1.2. for dose adjustments. Investigators may use their clinical judgment in modifying the schedule of eltrombopag if used as monotherapy or in combination with chemotherapy or disease modifying therapies to treat underlying MDS or AML.
- b. See Section 5.4.1. for dose escalation or reduction for further details.

#### **5.4.2. Cohort B and Cohort C (ITP Adults and Pediatric Subjects)**

Dose adjustments will be made as needed following the provided dosing guidelines for tablet formulation (Table 2 or Table 3) or suspension formulation (Table 4) and based upon each subject's individual platelet response. The target platelet count range for ITP patients is between 50 Gi/L and 200 Gi/L.

Investigators are expected to use their clinical judgment and knowledge about each subject's individual disease characteristics (including platelet count fluctuation and response to prior doses) for any dose adjustment.

The investigator should take into account any changes in concomitant ITP medications that could affect the platelet count when modifying the dose of eltrombopag.

If a subject has a platelet count that would require changing the dose to a dose that was previously proven to achieve platelet counts outside of the target range (<50 Gi/L or >200 Gi/L), alternating doses of different strength tablets or changes in frequency may be considered.

If a subject's platelet count increases significantly and if the investigator thinks a dose reduction is medically appropriate, the dose can be decreased even if the platelet count is below 200 Gi/L or a dose modification was done less than 2 weeks before.

If after an interruption the subject's platelet count decreases drastically and if the investigator thinks re-initiation is medically appropriate, the dose can be reinitiated at the next lower dose level even if the platelet count has not yet decreased to below 150 Gi/L.

If a subject's platelet count decreases drastically and the investigator thinks a dose increase is medically appropriate, the dose can be increased even if the platelet count is more than 50 Gi/L.

If dose increases or decreases are required based upon platelet counts, site personnel will instruct subjects on modified dosing instructions based upon the guidelines in Table 2 or Table 3. If dose adjustments are required based upon the dose adjustment guidelines, subjects must return the previous bottle(s) and may be dispensed new bottles containing 35 tablets each, or new cartons containing 35 sachets each.

The maximum dose for ITP subjects will be 75 mg once daily and must never exceed the maximum dose allowed by the parent study.

